4.1.2 Phase 2 Dose expansion

Patients with tumors demonstrating favorable PK and PD will proceed to Phase 2 Dose Expansion. In Dose Levels 1-3, patients will continue treatment with the same treatment level as given in Phase 0, patients should take the treatment continuously in 28d cycles with 3 weeks on / 1 week off after surgery. In Dose Level 4+, patients should take everolimus in one dose weekly; ribociclib will be taken for 21 consecutive days followed by 1 rest week. The dose will be per Table 7. If more than one DLT is observed in 6 patients in the Phase 2 dose expansion, the enrollment will be stopped and the previous lower dose level will be considered the RP2D and will be given for the remaining patients enrolled. If more than one DLT is occurred with the Level 0, the study will be stopped due to toxicity. Typically DLTs are defined by 1 cycle of treatment, which is 28 days. Since Phase 0 treatment is given for only 5 days, Phase 0 dose escalation will only be determined by Phase 0 DLT rules unless determined otherwise by the DSMB. Patients will be treated until unacceptable toxicity is observed, or until disease progression as assessed by radiographic or clinical metrics. Preliminary rates of progression-free survival in patients with high-grade gliomas treated with ribociclib+everolimus will be measured through radiographic and clinical response metrics, specifically Response Assessment in Neuro-Oncology (RANO) criteria and investigator discretion. Phase 2 participants will return to the clinic to monitor safety per the schedule of events until treatment is ended and will then be contacted approximately every 3 months by letter or phone for collection of survival data. The start of follow up for long-term survival begins following completion of the Day 30 safety follow up call.. All Phase 0/2 participants will be followed for survival for up to 5 years.

Common Toxicity Criteria Adverse Event (CTC AE 4.03) will be utilized to review ribociclib+everolimus treatment effects in patients with brain tumors.

Trough steady-state blood samples will be obtained on days 1, 8, 15, and 22 of cycles 1 and 2 prior to the administration of ribociclib+everolimus on that day. Note: ribociclib+everolimus will be administered in the clinics on the clinic visit days to ensure the collection of trough level samples.

PHASE 2 STUDY				
	Cycle 1 (28 d)	Cycle 2 (28d)	Subsequent cycles (28d)	End of study
Day of cycle	D1, D8, D15, D22	D1, D8, D15, D22	N/A	N/A

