6.1.1 Phase 0 & 2 Dose Escalation Schedule

Table 7 Dose Escalation Schedule

Dose Level	Phase 0 Dose of Study Drug ^a	Minimum Number of Patients	Phase 2 Dose of Study Drug ^a
0	ribociclib 400mg and everolimus 2.5mg	6	ribociclib 400mg and everolimus 2.5mg
1	ribociclib 600mg and everolimus 2.5mg	3	ribociclib 600mg and everolimus 2.5mg

Initial Version date: 10/16/2018

Revision date: 03/11/2019, 5/07/2019, 09/26/2019, 03/17/2020, 08/26/2024

Dose Level	Phase 0 Dose of Study Drug ^a	Minimum Number of Patients	Phase 2 Dose of Study Drug ^a
2	ribociclib 600mg and everolimus 5mg	3	ribociclib 600mg and everolimus 5mg
3	ribociclib 600mg and everolimus 10mg ^b	3	ribociclib 600mg and everolimus 10mg ^c
4	ribociclib 600mg, qd and everolimus 50mg once ^d	3	ribociclib 600mg daily and everolimus 50mg once weekly ^e
5	ribociclib 600mg, qd and everolimus 60mg once ^d	3	Cycle 1: ribociclib 600mg, qd and everolimus 50mg once weekly ^e Cycle 2+: 600 mg, qd and everolimus 60mg once weekly ^f
6	ribociclib 600mg, qd and everolimus 70mg once ^d	3	Cycle 1: ribociclib 600mg, qd and everolimus 50mg once weekly ^e Cycle 2: 600 mg, qd and everolimus 60mg once weekly ^f Cycle 3+: 600 mg, qd and everolimus 60mg once weekly ^f

- a. The Phase 0 dose given to the patient will be the RP2D. If more than one DLT is observed in 6 patients in Phase 2, the regimen at that given level will be considered as the maximal administered dose and the next lower dose level will be the MTD/RP2D for subsequent patients enrolled into Phase 2
- b. In Phase 0, the everolimus dose will be given in one dose (10mg, qd).
- c. In Phase 2, dose will be given in two doses (5mg, bid)
- d. In Phase 0, the everolimus dose will be given in one dose on Day 5 only; ribociclib dose will be given daily for 5 days.
- e. In Phase 2, everolimus dose will be given once weekly on Days 1, 8, 15, 22 of each cycle with ribociclib administered daily for 21 consecutive days and 1 rest week.
- f. If the dose is well tolerated in Cycle 1, the dose may be escalated based on investigator discretion.

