6.1.2 Phase 0 Dose Limiting Toxicity (DLT) and Maximum Tolerated Dose (MTD)

Dose escalation will proceed according to the following scheme for Phase 0:

Table 8 Phase 0 Dose Escalation Schedule - DLT and MTD

Number of Patients with DLT at a Given Dose Level	Escalation Decision Rule

Initial Version date: 10/16/2018

Revision date: 03/11/2019, 5/07/2019, 09/26/2019, 03/17/2020, 08/26/2024

0 out of 3	Enter 3 patients at the next dose level.
≥ 2	Dose escalation will be stopped. This dose level will be declared the maximally administered dose (highest dose administered). Three (3) additional patients will be entered at the next lowest dose level if only 3 patients were treated previously at that dose.
1 out of 3	Enter at least 3 more patients at this dose level. 
 • If 0 of these 3 patients experience DLT, proceed to the next dose level. • If 1 or more of this group suffer DLT, then dose escalation is stopped, and this dose is declared the maximally administered dose. Three (3) additional patients will be entered at the next lowest dose level if only 3 patients were treated previously at that dose and the lower dose level demonstrated positive PK/PD results (OBD).
≤ 1 out of 6 at highest dose level below the maximally administered dose	This is generally the recommended phase 2 dose (RP2D). If Dose Level 3 is reached, ≤ 1 out of 6 have experienced DLTs and the dose level has demonstrated positive PK/PD results, the time cohort will be expanded.

If one patient develops a DLT out of three, then the cohort will be expanded to include a total of 6 patients. If greater than or equal to two patients develop DLT, then that dose level will be considered the maximum administered dose (MAD) and further dose escalation will be terminated. A total of 6 patients will be treated at the next lower dose. The maximum tolerated dose (MTD) will be the dose at which no more than 1 patient develops DLT when at least 6 patients have been treated.

At the time of dose escalation, a written report will be submitted to the DSMB Chair (or qualified alternate) describing the cohorts, dose levels, adverse events, safety reports and any DLTs observed. The DSMB Chair will review the report and provide a written authorization to proceed or request more information within 2 business days. Approval for the dose escalation must be obtained prior to implementation.

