6.1.5 Guidelines for continuation of treatment beyond tumor resection (Optional Phase 2)

Patients with positive PK and PD responses will be provided the option of continuing on therapy until tumor progression. PK data evaluates the drug concentration in enhancing and non-enhancing region of the tumor. PD analysis evaluates the biomarker response after 5-day treatment and compares this with archival tissue. If both are positive the patients will be enrolled into Phase 2 portion of the trial with the same dose level taken during Phase 0 (unless there is more than one DLT observed in Phase 2, see Section 4.1.2). If the PD data is not conclusive due to treatment effect or limited tissue samples from the surgery, the PK data would be the primary guidance on deciding phase 2 enrollment.

Some anticipated risks and safety considerations of the ribociclib+everolimus combination will be closely monitored. Preclinical and Phase I clinical data available from ongoing studies with ribociclib and everolimus separately suggest few overlapping toxicities for the proposed

Initial Version date: 10/16/2018

Revision date: 03/11/2019, 5/07/2019, 09/26/2019, 03/17/2020, 08/26/2024

combinations. Special attention will be paid to blood counts (cytopenias), mucositis, liver function test abnormalities and QTc prolongation. Clinical data from the [CLEE011X2101] study do not show marked accumulation in ribociclib with time, suggesting that it does not substantially inhibit its own metabolism or clearance. Everolimus and ribociclib are *in vitro* inhibitors and substrates of CYP3A4, and the latter is also a time-dependent CYP3A4 inactivator. The available preclinical and clinical data therefore suggest the possibility of a drug interaction, specifically one that may increase exposure to everolimus. Based on simulation using Simcyp software (Simcyp Version 12, release 1), the projected increase in the AUC_{0-6h} of everolimus was 3.5-fold following the starting daily dose of 200 mg ribociclib co-administered with 2.5 mg of everolimus for 14 days. No significant effect on ribociclib metabolism was predicted when co-administered with everolimus. Appropriate eligibility criteria, dose modification guidelines and stopping rules are included in this protocol.

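### RP2D has two incompatible definitions, and the Phase 2 dosing rule makes no exception for a level stopped on Phase 0 DLTs

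*Combined protocol and SAP*

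**What the plan says.** **Two definitions of RP2D.** Table 7 note a (section 6.1.1) makes it specific to the patient: "The Phase 0 dose given to the patient will be the RP2D". Its next sentence lowers the dose for later Phase 2 patients only if more than one DLT occurs among 6 patients in Phase 2. Table 8 (section 6.1.2) works at trial level. Two or more patients with a DLT at a level stop escalation and make that level the maximally administered dose. Of the level beneath it, with no more than 1 of 6 having a DLT, Table 8 says: "This is generally the recommended phase 2 dose (RP2D"). Section 6.1.6 says that Phase 2 patients receive the RP2D and does not say which one. RP2D is also a listed secondary endpoint (sections 3 and 9.6).

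**The dose assigned to a PK/PD-positive patient.** Under section 6.1.5, "the patients will be enrolled into Phase 2 portion of the trial with the same dose level taken during Phase 0", with more than one Phase 2 DLT as the sole exception. Section 4.1.2 agrees: "In Dose Levels 1-3, patients will continue treatment with the same treatment level as given in Phase 0", and for Level 4 and above, "The dose will be per Table 7". For Level 4 that row reads "ribociclib 600mg daily and everolimus 50mg once weekly". Levels 5 and 6 start Phase 2 at 50 mg weekly. Table 7 note f then allows an increase, at the investigator's discretion, if Cycle 1 was well tolerated.

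**The link between the phases.** Section 4.1.2 says that "Phase 0 dose escalation will only be determined by Phase 0 DLT rules unless determined otherwise by the DSMB". That governs escalation. It does not say what happens to the Phase 2 dose of patients already treated at a level that Phase 0 then stops.

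**The concern.** Phase 0 can stop a level on DLTs seen within 5 days, and the same plan can then start or raise a patient to that level in repeated 28-day cycles. The note a definition permits this; the Table 8 definition would not. A site reading section 6.1.5 and a site reading Table 8 with section 6.1.6 could give different doses to the same patient.

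The reported endpoint is also affected. Under note a, PK/PD-positive patients from different levels each have their own RP2D, so the trial has no single RP2D to report. That holds even if no level is ever stopped.

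**Working it through.** **1. The plan's own threshold.** Section 3 defines the MTD with a 17% DLT limit. Table 8 allows 1 of 6: 1/6 = 16.7%, which passes. 2/6 = 33.3%, which exceeds 17% and is not below the one-third limit of section 6.1.3. So the threshold and the Table 8 rule agree, and a level with two patients having a DLT has failed Phase 0.

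**2. What each definition gives if the patient's own level is stopped.** Inputs are the Table 7 rows and notes c, e and f. Everolimus per 28-day cycle is 5 mg × 2 × 21 days = 210 mg at Level 3, 50 mg × 4 (Days 1, 8, 15, 22) = 200 mg at Level 4, and 60 mg × 4 = 240 mg at Level 5 from Cycle 2.

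| Level stopped in Phase 0 | Own-level rule (6.1.5, 4.1.2, Table 7) | Next lower level (Table 8 RP2D) | Do they differ? |
|---|---|---|---|
| 4 | 50 mg weekly, 200 mg per cycle | 5 mg twice daily for 21 days, 210 mg per cycle | From Cycle 1 |
| 5 | 50 mg weekly, then 60 mg (200, then 240 mg) | 50 mg weekly (200 mg) | From Cycle 2, if note f is used |
| 6 | 50, then 60, then 60 mg weekly | 50, then 60 mg weekly | No, as printed |

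The 50 mg start at Levels 5 and 6 is not in conflict, because 50 mg must have passed Phase 0 for those levels to open. For the lower levels the conflict appears to be only on paper: section 2.3 reports no adverse events that limited dosing before the high-dose levels were added.

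**3. How large the difference is at Level 4.** Ribociclib is 600 mg daily for 21 days at both Level 3 and Level 4. Everolimus per cycle is 200 mg against 210 mg. The contrast is therefore in single-dose size (50 mg against 5 mg) and schedule, not in the total.

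**4. How many patients.** Table 8 leaves 3 to 6 patients at a stopped level. The 8-patient time-cohort expansion requires fewer than 2 DLTs in 6 (section 6.1.2.1), so it adds none. Section 9.7.1 assumes PK/PD response in at most 50%: 0.5 × 6 = 3 at the upper end. Zero is possible, since 50% is a ceiling and Phase 2 is optional. The range is 0 to 3, against 3 to 12 planned for Phase 2.

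**5. Whether the Phase 2 step-down would catch it.** The trigger is more than one DLT, read here as at least two patients with a DLT at the level. If Level 4 is stopped, no higher level opens, so only its own 0 to 3 entrants receive 50 mg weekly. The trigger cannot fire with 0 or 1 entrant, and otherwise needs 2 of 2 or at least 2 of 3.

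**6. How likely a stop is.** The documents give no DLT rate. For an assumed chance p that a patient has a DLT counted in the window, P(stop) = 1 − [(1 − p)³ + 3p(1 − p)⁵].

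| Assumed p | 10% | 17% | 25% | 33% |
|---|---|---|---|---|
| P(level stopped) | 0.09 | 0.23 | 0.40 | 0.57 |

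At Level 4 and above, everolimus is given once, on Day 5 (Table 7 note d), and the Phase 0 window is the first 5 days (section 6.1.3). Several Table 9 criteria need 48 hours to more than 7 days to be met. The counted p for everolimus toxicity should therefore be low.

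**The case against.** A reader might infer that the plan leaves the Phase 2 dose undefined for these patients. The documents do not support that: section 6.1.5, section 4.1.2 and Table 7 all assign the patient's own level. The gap is a missing exception to a stated rule, plus a clash of terms.

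A reader might also be struck that Cycle 1 at Level 4 gives four times the everolimus of Phase 0 (200/50 = 4.0) and 4.2 times the ribociclib (12,600/3,000). Those ratios only reflect 5 days against a 28-day cycle. Level 3 has much the same: everolimus 210/(10 × 5) = 4.2, and identical ribociclib. They are not evidence of extra hazard at a stopped level.

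The stronger objections are these:

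- Table 8 is a Phase 0 rule, says only that its level is generally the RP2D, and section 6.1.3 judges the MTD within each phase. Letting a patient who personally tolerated the dose continue under Phase 2 DLT monitoring can be defended.
- Section 6.2 requires interruption for Grade 3 toxicity and, with limited exceptions, no further treatment after Grade 4. The DSMB reviews safety throughout and can recommend changes (section 8.6).
- Any fallback has a drawback. Level 3 returns to daily everolimus, the approach section 2.3 moved away from because of poor PK. The lower weekly doses in Table 10 have not been studied in Phase 0.

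The last point stands, and so no particular fallback is insisted on here. The first two limit the size of the concern but do not remove it. Judging the MTD by phase does not state a starting dose after a Phase 0 stop. Section 6.2 acts once a patient has toxicity. The protocol gives the DSMB no default dose, and its charter is a separate document that was not available.

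**Conclusion.** The point holds in a limited form. RP2D carries two meanings that cannot both be reported. The assigned-dose rule, read as written, lets a PK/PD-positive patient start (Level 4, 50 mg weekly from Cycle 1) or escalate to (Level 5, 60 mg weekly from Cycle 2 under note f) a level that Phase 0 declared the maximally administered dose.

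The practical reach is small: 0 to 3 patients at a stopped level, and a stop that the Day 5 dose and 5-day window make unlikely. This rests on the 50% ceiling in section 9.7.1, on Table 8 being followed as printed, and on section 2.3's account that earlier levels were not limited by toxicity. The probability of a stop cannot be estimated from the documents.

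It is still worth correcting, because it concerns the starting dose in a safety-driven escalation and the definition of a named endpoint.

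One related item needs confirmation. Level 6 is printed as 60 mg weekly from Cycle 3, while section 2.3 aims at 70 mg weekly and Table 10 has a 70 mg row. If 70 mg was intended, the same gap would open at Level 6.

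**What to change.** Make these wording changes by amendment:

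- Keep Table 8's RP2D as the only definition, and state in section 6.1.6 that this is the meaning.
- Rename the dose in Table 7 note a the assigned Phase 2 dose.
- Add one sentence to sections 6.1.5 and 4.1.2 and to Table 7 notes a and f: no patient starts, or escalates to, a Phase 2 dose at a level that Table 8 has declared the maximally administered dose.
- State the replacement dose for patients from a stopped level, as set by the sponsor and DSMB. For Level 4 the candidates already in the plan are Level 3 or a reduced weekly step from Table 10 (40 mg or 25 mg).
- Reconcile the Level 6 Cycle 3+ dose in Table 7 with section 2.3.

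No patients or assessments are added. The cost is that, if a level is stopped, one or two PK/PD-positive patients may continue at a lower dose or not continue.

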6.1.2.1 Optimal Biological Dose (OBD)

If positive tumor PK and PD effects are observed in patients treated at a specific dose, but no DLT is observed, dose escalation will continue as planned in order to demonstrate whether an increase in biological effect can be observed with increasing dosage or if such effect is maximized (ie, the OBD is attained). If the OBD has been achieved with <2 DLTs out of 6 patients, the OBD cohort will be expanded to an additional 8 patients to assure safety and to evaluate time course of PK and PD effects at 2 time cohorts (i.e., 2 ± 1 h and 24 ± 1 h), with 4 patients in each time cohorts, following the administration of the final dose on Day 5.

6.1.3 Dose Limiting Toxicity for Phase 0 or Phase 2

Dose limiting toxicity (DLT) will be defined as adverse event(s) which is/are attributable to the study treatment and unrelated to disease, disease progression, inter-current illness, or concomitant medications during the first 5 days in Phase 0 or in the first cycle (28 days) of Phase 2. The

maximum tolerated dose of ribociclib+everolimus will be that dose at which fewer than one-third of patients experience a dose limiting toxicity within each Phase. If multiple toxicities are seen, the presence of dose limiting toxicity should be based on the most severe toxicity experienced.

Table 9 DLT Criteria

TOXICITY	DLT CRITERIA
Hematology	CTCAE grade 4 neutropenia for more than 7 consecutive days CTCAE grade 4 thrombocytopenia CTCAE grade 3 thrombocytopenia with bleeding Grade 4 granulocytopenia lasting ≥ 5 days without hematopoietic growth factor support Febrile neutropenia (decrease in neutrophils associated with fever ≥ 38.5°C, ANC < 1.0 x 10 ⁹ /L)
Gastro-intestinal	≥ CTCAE grade 3 vomiting or nausea ≥ 48 hrs despite optimal anti-emetic therapy ≥ CTCAE grade 3 diarrhea ≥ 48 hrs despite optimal anti-diarrhea treatment
Hepato-biliary	CTCAE grade 2 bilirubin for more than 7 consecutive days ≥ CTCAE grade 3 total bilirubin ≥ CTCAE grade 2 ALT with a ≥ grade 2 bilirubin elevation of any duration in the absence of liver metastases ≥ CTCAE grade 3 ALT for more than 4 consecutive days CTCAE grade 4 ALT or AST CTCAE grade 4 serum alkaline phosphatase > 7 consecutive days
Cardiac	Cardiac toxicity ≥ CTCAE grade 3 Clinical signs of cardiac disease, such as unstable angina or myocardial infarction, or Troponin ≥ CTCAE grade 3
ECG QT Interval	QTcF interval ≥ 501 ms on at least two separate ECGs
Renal	≥ CTCAE grade ≥ 3 serum creatinine

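### After a Phase 2 stop at weekly Level 4, daily Level 3 becomes the RP2D with no 28-day DLT data required at Level 3

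*Combined protocol and SAP*

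**What the plan says.** Two places set the consequence of more than one DLT in 6 Phase 2 patients. Table 7 note a (6.1.1) says that "the regimen at that given level will be considered as the maximal administered dose and the next lower dose level will be the MTD/RP2D", and limits this to patients subsequently enrolled into Phase 2. Section 4.1.2 says that "the previous lower dose level will be considered the RP2D and will be given for the remaining patients enrolled"; it names the RP2D and not the MTD. Section 6.1.5 points to the same rule: patients continue on their Phase 0 level "unless there is more than one DLT observed in Phase 2".

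Levels 3 and 4 are adjacent rows of Table 7 but use different everolimus schedules. Level 4 in Phase 2 is 50 mg on Days 1, 8, 15 and 22. Level 3 in Phase 2 is 5 mg twice daily, three weeks on and one week off. In Phase 0, Level 3 is 10 mg once daily for 5 days. Ribociclib is 600 mg at both levels.

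Section 6.1.3 counts DLTs "during the first 5 days in Phase 0 or in the first cycle (28 days) of Phase 2". For Phase 0, 6.1.2 defines the MTD as "the dose at which no more than 1 patient develops DLT when at least 6 patients have been treated". Section 6.1.3 adds a general definition, "that dose at which fewer than one-third of patients experience a dose limiting toxicity within each Phase", with no minimum number of patients.

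**The concern.** A step-down rule normally relies on two things: the lower level is lower on the same scale, and it has been shown tolerable over the relevant period. At the boundary between Levels 4 and 3 the plan guarantees neither. The schedule changes, and nothing in note a or 4.1.2 requires that any patient has completed 28 days at Level 3 before it is named.

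Level 3 may have few or no Phase 2 patients. Section 2.3 explains the move to single high doses by persistently negative everolimus PK. This suggests, without establishing it, that few Level 3 patients met the PK/PD condition for Phase 2. Section 6.1.6 describes Phase 2 entry without that condition, so some Level 3 patients may exist.

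At stake are the RP2D that the trial reports and the regimen given to later Phase 2 patients. Section 4.1.2 says that "Phase 0 dose escalation will only be determined by Phase 0 DLT rules unless determined otherwise by the DSMB". Phase 0 could therefore continue at Levels 4 to 6 after a Phase 2 stop at Level 4, and patients who qualified on a single dose of 50 mg or more would then be given 5 mg twice daily.

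**Working it through.** **The plan's own threshold.** Sections 3 and 9.5 cap the MTD at a 17% DLT rate. The rule of at most 1 DLT in 6 gives 1/6 = 16.7%, which reproduces that figure.

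**Is Level 3 lower?** (doses from Tables 6 and 7)
- Phase 2 cycle, Level 3: 2 × 5 mg × 21 days = 210 mg.
- Phase 2 cycle, Level 4: 50 mg × 4 = 200 mg. Ratio 210/200 = 1.05, so Level 3 is 5% higher.
- Phase 0 totals: 10 × 5 = 50 mg against 50 × 1 = 50 mg.
- Per administration, Level 3 is much lower: 5 mg against 50 mg.

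The order of the two regimens therefore depends on the scale chosen.

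**What evidence must exist at Level 3?** The Table 7 minimum is 3 patients, and 0 of 3 with DLT permits escalation (Table 8).
- Observation: 3 × 5 = 15 patient-days, against 6 × 28 = 168 for six patients over the Phase 2 window.
- One-sided 95% upper bound after 0/3: 1 − 0.05^(1/3) = 0.632. This bounds the 5-day rate on 10 mg once daily, not the 28-day rate on 5 mg twice daily.
- Some Table 9 criteria cannot be completed within 5 days, such as grade 4 neutropenia lasting more than 7 days. Section 1.2.2.2.1 puts everolimus steady state on daily dosing at within two weeks.

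**Illustration of the gap.** The documents give no true DLT rate and no DLT timing, so both are assumed. Let p be the 28-day rate and p5 the 5-day rate.
- Constant hazard: p5 = 1 − (1 − p)^(5/28).
- Even spread: p5 = p × 5/28.
- All DLTs after Day 5: p5 = 0.
- P(0 of 3 in 5 days) = (1 − p5)^3.
- P(at most 1 of 6 in 28 days) = (1 − p)^6 + 6p(1 − p)^5.

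| p | 0/3, constant hazard | 0/3, even spread | 0/3, all late | ≤1/6 over 28 days |
|---|---|---|---|---|
| 20% | 0.887 | 0.897 | 1 | 0.655 |
| 33% | 0.805 | 0.832 | 1 | 0.351 |
| 50% | 0.690 | 0.755 | 1 | 0.109 |

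Under any of these timings, a clean 5-day result in 3 patients separates tolerable from intolerable 28-day rates far less well than the 6-patient criterion.

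**Will the gap close by itself?** Section 9.7.1 expects at most 12 Phase 2 patients. After 6 at Level 4, at most 12 − 6 = 6 remain. If the first 2 both have DLTs, at most 12 − 2 = 10 remain. Patients already used at other levels reduce both figures, so six at Level 3 may not be reached.

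**The case against.** The strongest reply is that note a is an assignment rule. It is limited to subsequent Phase 2 patients, and note a and 6.1.6 use RP2D largely as a label for the dose a Phase 2 patient receives. Those patients remain under the same limit of one DLT in 6. The DSMB chair must approve each escalation (6.1.2, 8.6.1), and the board can recommend modification or termination (8.6). All of this stands: no stopping rule is missing. But RP2D is also a listed secondary endpoint, and the text does not separate the dose assigned next from the dose reported at the end. The safeguards act after the level is named, or by discretion.

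A second reply is that the MTD already carries DLT conditions: the 17% cap, and the one-third limit of 6.1.3 within each phase. That is also correct. Neither sets a minimum number of Phase 2 patients, neither can be evaluated with none treated at Level 3, and neither is stated as a condition on the RP2D.

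Three stronger readings are tempting, and the documents do not support them:
- *The primary endpoint is compromised.* Section 9.7.1 assigns the primary MTD endpoint to Phase 0, where 6.1.2 requires at least 6 treated patients. Section 4.1.2 does not mention the MTD.
- *Level 3 is unsafe or more intense.* The 5% concerns cycle totals only, and each administration is smaller. Section 2.3 reports no dose-limiting adverse events, although it ties this neither to Level 3 nor to 28 days.
- *The fallback must require positive PK/PD.* Table 8 has that condition in its 1-of-3 row only; the row for two or more DLTs backfills without it. Imposing it could leave qualifying patients with no Phase 2 dose.

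**Conclusion.** The concern holds in a limited form. As written, a Phase 2 stop at Level 4 names Level 3 the RP2D (and, in note a, the MTD/RP2D for later Phase 2 patients) with no required 28-day DLT data. The move is to a different everolimus schedule whose cycle total is 210 mg against 200 mg. The minimum support is 3 patients over 5 days on a different daily split of the dose.

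The consequence is a possibly unsupported secondary endpoint and an untested dose for a handful of later patients. DLT counts by level remain interpretable, and the Phase 0 MTD is unaffected. The issue arises only if at least 2 Phase 2 patients at Level 4 have DLTs. The dose totals and the 63% bound follow from the plan's figures; the probabilities in the table rest on assumed rates and timing and only illustrate the point. Severity: minor to should-fix.

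**What to change.** Amend Table 7 note a and 4.1.2 to state that:
1. a Phase 2 stop at Level 4 establishes no MTD or RP2D for the weekly schedule;
2. the fallback level is a provisional dose for later Phase 2 patients;
3. it is reported as the Phase 2 MTD/RP2D only with no more than 1 DLT in at least 6 patients over the 28-day window, counting earlier Phase 2 patients at that level; otherwise the RP2D is reported as not determined.

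No PK/PD gate need be added. The sponsor may consider stepping down within the weekly schedule instead. Table 10 already lists 40 mg weekly as the reduction from Level 4 (4 × 40 = 160 mg per cycle), which is lower both per dose and per cycle.

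The cost is wording in two places, using a criterion the protocol already applies in Phase 0. No accrual beyond the plan is needed. The downside is that the trial may end without a declared RP2D.
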